6.3 Outcome measures

To ensure the correct outcome domains are being collected, we have undertaken an exercise to ratify the outcomes collected in this trial. A systematic review identified 52 outcome domains that have been previously used to record success/failure in medial epicondyle fractures. A Delphi process considered the views of 25 physiotherapists, 39 UK children's orthopaedic surgeons, 17 surgeons from international orthopaedic trials groups, 20 parents of affected children and 10 affected children. The most important outcome domains are now apparent in the final stages of formalising the Core Outcome Set.

Core Outcomes apparent from Delphi exercise:

• Activities of Daily Living (ability to dress/wash/eat).

20JUN2024 | V7.0

- Participation in School Activities
- Ability to resume participation in hobbies and sports.
- Pain
- Complications (Nerve Injury, infection, metalwork prominence, review of any available routinely collected digital images of the elbow stored in the PACS archive).

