8.3 Reporting Procedures for Complications

Complications (i.e. AEs and SAEs that are anticipated in the routine treatment pathway, and that we have predefined) that are foreseeable in the treatment of these fractures do not need to be reported immediately, provided they are recorded in the 'Complications' section of the Case Report Forms and/or Patient Questionnaires. For this trial, such events include the following complications (including readmission or reoperation to address them):

(a) General complications – pain, pressure areas or elbow stiffness, symptomatic instability or nonunion of the bone fragments

(b) Complications specifically related to surgery - wound infection, injury/irritation to the ulna nerve, implant irritation, screw cut-out, broken or retained metalwork and the subsequent need to remove metal pins/ screws.

9. Data Management

The data management aspects of the study are summarised here with full details described in the Data Management Plan (DMP).

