Subgroups analyses will be undertaken with the aim of exploring the consistency of treatment effects across important baseline characteristics. These include age-groups (8+ or younger), initial immobilisation duration and dislocation status will be explored using treatment by subgroup interactions [15]. Forest plots with 95% confidence interval will be used to present the subgroup analysis results. Secondary clinical outcomes and patient reported outcomes will be similarly analysed using mixed effects regression, using logistic regression for binary data and linear regression for continuous data.

Any subsequent changes in this plan are strongly discouraged. If any changes to this SAP are implemented these will be documented in an updated version of this SAP. Documentation of any such changes will include the rationale for the changes, and when and by whom these were agreed.

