Particular note will be made of complications related to the cast (e.g. pressure areas) or surgery (e.g. pain, wound infection, injury/irritation to the ulna nerve, implant irritation, screw cut-out, broken or retained metalwork, and the subsequent need to remove metal pins/screws), including hospital admission to manage these complications. These are summarised in the Table below.

Table 10: Comparison of complications & SAEs between treatment allocations

| | Operative fixation | Non-operative treatment | | OR (95 | 5% CI) | p- value |
|--|-----------------------|----------------------------|---|--------|--------|-------------|
| | n % | n | % | Raw | Adj. | |
| Number of complications* | - | | - | - | - | - |
| Participants with complications | | | | | | |
| Wound problems (from surgery*) | | | | | | |
| Elbow stiffness | | | | | | |
| Unable to move fingers normally | | | | | | |
| Patient Reported concerns | | | | | | |
| Unable to feel fingers normally | | | | | | |
| Ulna nerve problems (little & ring | | | | | | |
| fingers) | | | | | | |
| Other | | | | | | |
| Intra-operative complications | - | | - | - | - | - |
| Participants with intra-operative | | | | | | |
| complications | | | | | | |
| Ulna nerve injury | | | | | | |
| Fragmentation of bone | | | | | | |
| Wire breakage | | | | | | |
| Anaesthesia complications | | | | | | |
| Post-operative bleeding | | | | | | |
| Screw cut-out | | | | | | |
| Other | | | | | | |
| Immobilisation complications | - | | - | - | - | - |
| Participants with immobilisation | | | | | | |
| complications | | | | | | |
| Skin complication owing to pressure | | | | | | |
| area | | | | | | |
| Discomfort | | | | | | |
| Other | | | | | | |
| Unplanned surgery/hospital | - | | - | - | - | - |
| admissions* | | | | | | |
| Participants with unplanned | | | | | | |
| surgery/hospital admissions | | | | | | |
| Fracture fixation/ revision fixation | | | | | | |
| Removal of screw(s)/wire(s) | | | | | | |
| Planned removal | | | | | | |
| Irritation | | | | | | |
| Other | | | | | | |
| Nerve exploration (isolated | | | | | | |
| procedure) Nerve exploration & screw/wire | | | | | | |
| adjustment | | | | | | |
| Nerve exploration and grafting | | | | | | |
| Debride wound/ wound infection | | | | | | |
| Microbiological confirmation of | | | | | | |
| infection | | | | | | |
| Antibiotics prescribed | | | | | | |
| Other | | | | | | |

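### Table 10 leaves odds ratios and p-values open on rows that only an operated child can fill, and has no named row for symptomatic instability, nonunion or pain as a complication

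*SAP*

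**What the plan says.** SAP 6.1 presents harms in "Table 10: Comparison of complications & SAEs between treatment allocations". The columns are n and % by arm, raw OR, adjusted OR and p-value. The estimate cells carry dashes on the rows that count events and on the block headings. They are blank, and so open, on the participant and item rows. Open rows include "Participants with intra-operative" complications and the items beneath it, "Wound problems (from surgery"), and "Removal of screw(s)/wire(s") with its sub-rows.

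Four other parts of the SAP bear on those cells:
- Section 3.7 asks for 95% confidence intervals and 5% two-sided tests on all comparative outcomes, and plans mixed-effects models for secondary outcomes, "using logistic regression for binary data and linear regression for continuous data".
- Table 1 keeps children who switch treatment in the arm to which they were randomised.
- Section 6.5 has a minimum-count rule, but it covers subgroups only.
- Section 6.1 lists complications of particular note, including pain, implant irritation and broken or retained metalwork, and says the table summarises them.

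Protocol 8.3 pre-defines the foreseeable complications. The first group is ("a) General complications – pain, pressure areas or elbow stiffness, symptomatic instability or nonunion of the bone fragments". The second group is specific to surgery. Protocol 6.3 includes "Complications (Nerve Injury, infection, metalwork prominence" among the core outcomes. SAP 6.7 says that foreseeable, non-serious events are reported as outcomes through the Complications section.

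**The concern.** Secondary objective 5 is the complication rate, and Table 10 is where it will be read. There are two problems.

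1. Some rows describe events that require an operation or an implant. A between-arm OR on such a row compares a group that was mostly operated on with one that mostly was not. It says little about how risky the operation is, which is what a family considering surgery needs to know. No SAP rule tells the analyst to leave these cells empty, and none says what to do with zero or sparse cells.

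2. The table does not follow the protocol's own list. Symptomatic instability and nonunion are pre-defined complications, yet they could appear only under a generic 'Other' row. Pain is on both the protocol list and the SAP's list, and has no row as a complication.

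**Working it through.** **Denominators.** For a 4-point difference, SD 10, 90% power and 5% two-sided, the t-based solution is 132.3 per arm, so 133 (266 in total). Then 133 / 0.80 = 166.25, so 167 per arm (334 in total). This reproduces the plan's figures; 167 per arm is used below.

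**Rows affected.** As read from the PDF, Table 10 has about 34 rows with open OR and p cells. Those that need surgery or metalwork are 1 wound row, 8 intra-operative rows, 4 screw or wire removal rows, and 1 row for nerve exploration with screw/wire adjustment: 1 + 8 + 4 + 1 = 14. Adding the wound debridement and infection rows makes about 17.

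**What the OR measures.** Let r be the event risk in any child operated on, u the share of the operative arm not operated on, and s the share of the non-operative arm operated on. By allocation, the arm risks are (1 − u)r and s·r. So

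OR = [(1 − u)r / (1 − (1 − u)r)] / [s·r / (1 − s·r)], which is close to (1 − u)/s when r is small. The surgical risk r nearly cancels.

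The documents give no values for r, u or s. Assume r = 8% and u = 5%. Expected operative-arm events are 167 × 0.95 × 0.08 = 12.7, with odds 0.076/0.924 = 0.0823.

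| s (assumed) | Expected non-operative-arm events, 167 × s × 0.08 | Odds in that arm | OR |
|---|---|---|---|
| 0% | 0 | 0 | no finite estimate |
| 5% | 0.7 | 0.004/0.996 | 20.5 |
| 10% | 1.3 | 0.008/0.992 | 10.2 |
| 15% | 2.0 | 0.012/0.988 | 6.8 |

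Varying r from 2% to 10% with u = 0 gives an OR of 20.4 to 22.1 at s = 5%, 10.2 to 11.0 at s = 10%, and 5.1 to 5.4 at s = 20%. A fivefold change in surgical risk barely moves the OR; a change in switching moves it almost in proportion.

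**How often the cell is empty.** At s = 10% (17 children) and r = 5%, 17 × 0.05 = 0.85 events are expected in the non-operative arm, and the chance of none is 0.95^17 = 42%. A logistic OR then has no finite estimate. A p-value can still be produced: at 167 per arm, Fisher's exact test gives p = 0.061 for 5 v 0 and p = 0.030 for 6 v 0. The 0.5-corrected OR for 6 v 0 is 13.5 (95% CI 0.75 to 241).

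**Protocol 8.3 against Table 10.** The protocol lists 11 complications.

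| Protocol 8.3 item | Table 10 |
|---|---|
| Pressure areas, elbow stiffness, wound infection, ulnar nerve injury or irritation, screw cut-out, removal of metalwork (6) | Row present |
| Implant irritation | Only as a reason for removal |
| Broken or retained metalwork | Only as intra-operative wire breakage |
| Pain | No named row |
| Symptomatic instability | No named row |
| Nonunion | No named row |

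So 6 have a row, 2 are covered in part and 3 have no named row.

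**The case against.** The other side has several good points.

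- *Table 10 is an unfilled shell.* SAP section 1 says shell tables will be reviewed before the final analysis, and a blank cell is not a promise to print an OR. That is fair, and the review is the natural place to settle this. But section 3.7 points towards estimating every comparison and strongly discourages later changes, so the decision should be written down.
- *A by-allocation OR is a valid treatment-policy quantity.* This stands. A child allocated to non-operative treatment who is operated on can have these events, so the cell need not be zero. The OR is uninformative about surgical risk rather than wrong.
- *Pain is handled elsewhere.* This stands in part. Wong-Baker scores are compared between arms, and Table 10 has a discomfort row under immobilisation. Neither counts pain recorded as a complication.
- *Nonunion is handled elsewhere.* This also stands in part. SAP 6.1 sends radiographic outcomes to a separate document, and nonunion leading to fixation could enter the fixation row. Symptomatic instability is not a radiographic outcome, and neither route clearly covers "symptomatic instability or nonunion of the bone fragments" as recorded complications.
- *The text is imperfect.* Asterisks in the table point to a footnote that cannot be seen, and indentation is lost, so the row counts are approximate.

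A reader might infer that the whole harm comparison is wrong, or that the main harms of non-operative treatment cannot be seen. The documents do not support either. Counts and percentages by arm are valid. The stiffness, nerve, pressure-area and unplanned-fixation rows are proper comparisons that would show harm in either arm. A reader might also use the protocol's union figures (about 50% v 95%, section 5.2) to argue that the missing rows hide a large excess. Those figures are for bony union, not symptoms, and the same section says it is unclear whether union affects function.

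**Conclusion.** The point holds as a matter of layout and reporting. About 14 of some 34 open rows invite an OR and p-value that either cannot be estimated or mainly describe how many children in the non-operative arm were operated on: about 20, 10 and 7 at 5%, 10% and 15% switching. Those values rest on the assumed 8% event risk and 5% non-operated share. That the OR follows switching and hardly depends on surgical risk does not rest on those particular values, provided the event is uncommon and its risk is the same in every operated child.

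Three of the 11 complications pre-defined in Protocol 8.3 have no named row. The gap matters most for symptomatic instability and nonunion; for pain it is partly offset by the Wong-Baker comparison. Two more are counted only in part. The primary outcome and the sample size are not affected.

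**What to change.** Revise Table 10 and the accompanying text in SAP 6.1:

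1. Keep n and % by allocation on every row.
2. On surgery-only rows (intra-operative complications and their items, wound problems from surgery, screw or wire removal, and other rows that need metalwork), remove the OR and p-value. Add n/N of children operated on with an exact 95% CI, labelled descriptive and by treatment received.
3. Keep between-arm estimates for events that either arm can have, such as stiffness, nerve symptoms, pressure-area problems, unplanned fixation and unforeseeable SAEs.
4. Add rows for symptomatic instability, symptomatic nonunion, pain as a complication, implant irritation whether or not the implant is removed, and post-operative broken or retained metalwork. Alternatively, state which CRF or questionnaire item each maps to and where it will be reported.

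The cost is SAP and table wording, a longer table, fewer p-values, and a non-randomised denominator on the surgery-only rows, which is why they must be labelled as descriptive. Protocol 8.3 expects these events to be recorded on the CRF or questionnaires, but the documents do not show the individual items. Check that each item can be separated before committing to its row; where it cannot, say so in a table note.

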10.1 Statistical Analysis

A separate statistical analysis plan (SAP) with full details of all statistical analyses planned for the data of this study will be drafted early in the trial and finalised prior to any primary outcome analysis. The SAP will be reviewed and will receive input from the TSC and the DSMC. Any changes or deviations from the original SAP will be described and justified in the protocol, final report and/or publications, as appropriate. It is anticipated that all statistical analysis will be undertaken using Stata (StataCorp LP, www.stata.com) or other well-validated statistical packages. All analyses will be carried out on the intention-to-treat population (that is all patients will be analysed in the group they were randomised to regardless of actual treatment received. The analyses will be repeated for the per protocol population (patients excluded from the per-protocol population will be pre-specified in the SAP as a sensitivity analysis to test the robustness of the results). Sensitivity analyses that supplement the primary analysis will include repeating the primary analysis for the per protocol population and the astreated population, bearing in mind that this may introduce bias by losing the benefits of randomisation.

Missing Data: Although we have allowed for up to 20% missing data in the sample size we hope to minimise this by utilising data collection techniques appropriate to the age of participating children. Before carrying out the within trial analysis, we will check the trial data for any missing data. Where possible the reasons for missing data will be ascertained and reported. The nature and pattern of the 'missingness' will be carefully considered — including in particular whether data can be treated as missing at random (MAR). If judged appropriate, missing data will be imputed using multiple imputation. The resulting imputed datasets will be analysed and reported, together with appropriate sensitivity analyses.

Standard descriptive statistics will be used to describe the demographics between the treatment groups reporting means and standard deviations or medians and interquartile ranges as appropriate for continuous variables, and numbers and percentages for binary and categorical variables. All comparative outcomes will be presented as summary statistics and reported together with 95% confidence intervals and all tests will be carried out at a 5% two-sided significance level.

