| Treatment: Operative fixation vs non-operativ | e treatment |
|---|--|
| Estimand | Analysis |
| Target population | Analysis set |
| Children aged between 7 and 15 years who present at participating UK hospitals with a medial epicondyle fracture of the humerus. | All randomised participants. |
| Variable | Outcome measure |
| Physical Function measured on the child reported PROMIS Upper Extremity scale at 1-year post-randomisation. | Continuous outcome bounded scale (PROMIS Upper Extremity T-score) where higher scores indicate better function better function, at 12 months post-randomisation |
| Handling of intercurrent events | Handling of missing data |
| Switching Treatment arm: Participants who receive a different intervention to that which they were allocated will be analysed according to their randomised allocation Further surgery: Participants that require additional surgical intervention on their elbows are also considered part of the treatment All intercurrent events will be handled under a treatment-policy strategy ¹ . | Multilevel modelling of outcome scores over time, imputes implicitly intermittent missing data over the post- randomisation period of follow-up. The underlying assumption is missing at random (MAR) conditional on all other outcome scores and minimisation factors. This is the main approach to handling missing data. Sensitivity analysis : The MAR assumption can be strengthened by conditioning on additional baseline covariates predictive of the outcome and missingness. Missing data arising from participants discontinuing in the study prior to 12 months under a NMAR (Not Missing at random) informative missing data mechanism will be explored under two approaches: a) the extended Hausman-Wise-Diggle-Kenward selection model when drop out depends on outcome scores prior to drop out and where this is jointly modelled with the longitudinal outcome. b) using controlled multiple imputation: δ - based imputation (see section (Details in Section 6.3: Missing data) where the primary analysis model is augmented with an offset term with values set to the fixed values of the missing and repeated over |

a range (+/- 1 SD PROMIS score). This is done to assess the impact of drop-out on inferences

| Population-level summary measure | Analysis approach |
|---|---|

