3.7 Statistical Analysis Outline

It is anticipated that all the statistical analysis will be undertaken using Stata [14] although other well-validated statistical packages may be considered for statistical quality control validation analyses. All analyses will be carried out under a treatment policy strategy (that is, all patients will be analysed in the group they were randomised to regardless of actual treatment received. The analyses will be repeated for the per protocol

population(definition in section 4.2) as mandated by the protocol , bearing in mind that this may introduce bias by losing the benefits of randomisation and introducing ambiguity in the primary estimand of interest.

Although we have allowed for up to 20% missing data in the sample size, we hope to minimise this by utilising data collection techniques appropriate to the age of participating children. Before carrying out the within trial analysis, we will check the trial data for any missing data. Where possible the reasons for missing data will be ascertained and reported. The nature and pattern of the 'missingness' will be carefully considered — including whether data can be treated as missing at random (MAR). The handling missing data is detailed 6.3.

Standard descriptive statistics will be used to describe the demographics between the treatment groups reporting means and standard deviations or medians and interquartile ranges as appropriate for continuous variables, and numbers and percentages for binary and categorical variables. All comparative outcomes will be presented as summary statistics and reported together with 95% confidence intervals and all tests will be carried out at a 5% two-sided significance level.

The Patient Reported Outcomes Measurement Information System (PROMIS) Upper Extremity Score for Children at 12 months is the primary outcome of the study and the primary analysis will compare this between the treatment groups in a linear mixed effects method including all participant data, adjusting for the stratification factors. A simple analysis of covariance (ANCOVA) of the primary outcome at 12 months adjusting only for the baseline PROMIS score will be undertaken as a secondary analysis.

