4.2 Definition of Analysis Populations

Populations for analysis are defined as follows:

- Intention-to-treat (ITT): all participants analysed in their randomised groups, regardless of actual treatment received. This reflects the primary estimand of interest (treatment policy).
- Per-Protocol (PP): participants who received the intervention as intended will be analysed according to the treatment they actually received. Participants will be excluded from the per-protocol population if:

- They did not receive the treatment allocated through randomisation
- o They did not fully satisfy the eligibility criteria for the study

Blinded review of the protocol deviation data (not separated by treatment arm) which may affect the PP analyses will be undertaken prior to the final data lock. A summary of the characteristics of exclusions to define the per-protocol population will be reported. The motivation for any such exclusion is to examine the robustness of inferences to factors that can threaten the study's internal validity. Deviations associated with intercurrent events which occurred in the trial setting but would not be observed in practice are considered the main threat, consistent with the primary ITT estimand. If a significant number of such deviations are present e.g. involving more than >5% of participants, the results of the primary analyses may introduce ambiguity in the interpretation. In this case sensitivity analyses is undertaken and detailed in section 6.4.

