5.5 Treatment Compliance with Details of Intervention

The intervention groups in this trial are operative fixation or non-operative treatment of the medial epicondyle fracture of the elbow in children. As this is a one-off intervention, compliance is defined by the proportion of participants for each allocation that receive the treatment they were randomised to. The numbers and percentages of participants receiving each treatment are summarised, as well as those who did not receive the allocated treatment. Reasons are given in the cases where the participants did not receive the allocated treatment (Table 8).

Table 8: Compliance with allocated intervention

| Treatment Received | Operativ | e fixation | Non-operative treatment | |
|---|----------|------------|----------------------------|---|
| | n | % | n | % |
| Allocated Treatment | | | | |
| Other | | | | |
| Reasons for not receiving allocated treatment | | | | |
| Clinical decision | | | | |
| Child/Parent decision | | | | |
| Lack of equipment | | | | |
| Administrative error | | | | |
| Other | | | | |

Details of treatment received are summarised in Table 9.

Table 9: Information about Intervention Received

| | n | % |
|--|---|---|
| Operative Fixation: | | |
| Screws | | |
| Cannulated screws | | |
| Solid screws | | |
| Wires | | |
| Buried | | |
| Unburied | | |
| Other | | |
| Non-Surgical treatment: | | |
| Above elbow full cast | | |
| Above elbow back slab | | |
| Other splint | | |
| Bandage | | |
| Other | | |
| Post-Intervention Instructions: | | |
| Cast off at X weeks | | |
| Operative Fixation | | |
| Non-Surgical treatment | | |
| Immediate mobilisation as tolerated, with physiotherapy | | |
| Operative Fixation | | |
| Non-Surgical treatment | | |
| Immediate mobilisation as tolerated, without physiotherapy | | |
| Operative Fixation | | |
| Non-Surgical treatment | | |
| Rest until X weeks | | |
| Operative Fixation | | |
| Non-Surgical treatment | | |
| Other | | |
| Operative Fixation | | |
| Non-Surgical treatment | | |

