6. ANALYSIS

The primary estimand of interest will be a treatment policy estimand (ITT population), using data from all randomised participants as randomised. This is chosen as the primary estimand to reflect the pragmatic nature of the study, and to identify the treatment effect regardless of any intercurrent events occurring. The elements of the primary estimand are summarised in Table 1.

The protocol also mandates a per-protocol analysis. The per-protocol analyses (section 4.2) will include all randomised participants who received their allocated treatment but excludes those randomised participants who were found ineligible post-randomisation, did not receive their allocated treatment.

Treatment switching as defined by NICE refers to the situation in a randomised controlled trial where patients switch from their randomly assigned treatment onto an alternative. Although it is widely recognised that ITT does not identify the true comparative effectiveness of the treatments under investigation there is disagreement on the acceptability of adjustment methods that can be used. Following NICE recommendations our ITT analyses is supplemented with further analyses in an attempt to adjust for switching [16] and described in section 6.4 sensitivity analyses.

The primary analysis and sensitivity analysis described in sections 6.2-6.4 focus on the primary estimand detailed in Table 1 which targets the average difference in PROMIS scores (ATE) between the two interventions in the combined groups randomised to receive each intervention. The resulting treatment effect represents the average difference in PROMIS scores we can expect if all participants in the target population were treated with non-operative treatment instead of being treated with operative fixation [17-19].

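### Complications are tabulated by allocation and per protocol but never by treatment received, so a surgical harm in a child who crossed from cast to surgery enters no rate among operated children

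*SAP*

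**What the plan says.** Complications are a secondary outcome. Protocol 6.2.2 (objective 5) asks for the complication rate, including further operative fixation, up to one year.

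- **Table 10 (SAP 6.1)** is headed "Table 10: Comparison of complications & SAEs between treatment allocations". It has n and % for each arm, raw and adjusted odds ratios, and a p-value.
- **Main analysis principle (SAP 3.7):** "All analyses will be carried out under a treatment policy strategy". Table 1 of the SAP adds: "Participants who receive a different intervention to that which they were allocated will be analysed according to their randomised allocation". It also counts further elbow surgery as part of the treatment.
- **Second analysis set (SAP 3.7):** "The analyses will be repeated for the per protocol" population. SAP 4.2 excludes participants if "They did not receive the treatment allocated through randomisation". SAP 6 says this analysis "will include all randomised participants who received their allocated treatment".
- **As-treated population:** Protocol 10.1 plans "repeating the primary analysis for the per protocol population and the astreated population". This concerns the primary analysis only, and the SAP does not carry it over.
- **Treatment received (SAP 5.5):** "The numbers and percentages of participants receiving each treatment are summarised". This is done in Tables 8 and 9, which contain no complications.
- **Table 11 (SAP 6.7)** lists serious adverse events with allocation and causality columns, and has no column for treatment received.

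**The concern.** Families and clinicians will read the complications table for two things: what follows from choosing each strategy, and what the risk is if a child has the operation. The plan supports the first and has no table for the second.

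Take a child allocated to a cast who is operated on and has a surgical complication. By allocation, the event sits in the non-operative column and pulls the odds ratio towards 1. Per protocol, the child is left out. SAP 4.2 says per-protocol participants are analysed by the treatment they actually received, but once switchers are excluded this is the same as allocation. In neither set does the event enter a numerator over operated children.

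The SAP plans a propensity-score analysis for switching (6.4), but only for the PROMIS score. Harms have no counterpart.

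**Working it through.** **Arm size.** With a 4-point difference, SD 10, two-sided 5% and 90% power, the normal formula gives 132 per arm. The two-sample t version gives 132.3, so 133 per arm (266 in total). Allowing for 20% loss, 133 / 0.8 = 166.25, so 167 per arm (334 in total). The plan's figures reproduce, and 167 per arm is used below.

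**Assumptions.** The documents give no switching rate and no surgical complication rate. Let r be the risk of a surgery-caused complication if operated on (zero if not), a the proportion going from cast to surgery, and b the proportion going from surgery to cast. Switchers first carry the same risk as other operated children. Table 10 states no denominators; for the illustration, all allocated children are used.

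**Formulas, with N = 167.**
- By allocation: operative column N(1−b)r events, non-operative column N·a·r events, risk difference r(1−a−b).
- Per protocol: operative N(1−b)r out of N(1−b), which equals r; non-operative 0 out of N(1−a). The share of surgical events left out is a / (1−b+a).
- By treatment received: N(1−b+a)r out of N(1−b+a), which equals r.

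| r, a, b | Operative column | Non-operative column | Risk difference by allocation | Surgical events left out per protocol | Operated children, treatment received |
|---|---|---|---|---|---|
| 5%, 5%, 0% | 8.35/167 (5.0%) | 0.42/167 (0.25%) | 4.75 points | 4.8% | 8.8/175 (5.0%) |
| 10%, 10%, 5% | 15.9/167 (9.5%) | 1.7/167 (1.0%) | 8.5 points | 9.5% | 17.5/175 (10.0%) |
| 20%, 20%, 10% | 30.1/167 (18.0%) | 6.7/167 (4.0%) | 14.0 points | 18.2% | 36.7/184 (20.0%) |

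The first and last rows give the ends of the range for events in the cast column (0.4 to 6.7) and for the share left out per protocol (4.8% to 18.2%). By allocation, the risk difference shrinks by the sum of the two switching rates as a fraction of r. At r = 10% it runs from 9.5 to 7.0 points.

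**Per-protocol rate.** In the middle row it is 15.9/159 = 10.0%, the same as by treatment received, because events and denominators leave together. The two differ only if switchers' risk differs. If switchers' risk were 20% against 10% in the others, their events would be 16.7 × 0.20 = 3.3. The rate by treatment received would then be (15.9 + 3.3)/175.35 = 11.0%, against 10.0% per protocol.

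**Which rows identify the cause.** In Table 10 the intra-operative, surgical-wound and screw or wire removal rows can only refer to surgery, whichever column they fall in. Elbow stiffness, ulna nerve problems, abnormal finger movement or feeling, and the general 'other' row carry no cause. For these, the reader cannot tell which treatment the child had.

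**The case against.** The case against rests on five arguments.

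- **No event is lost.** A reader might infer that a switcher's surgical harm vanishes or is never shown as surgical. The documents do not support that. The allocation table is always reported, the per-protocol version is an addition to it, and several rows name the cause. This stands.
- **The surgical risk need not be understated.** If switchers have the same risk, the per-protocol rate among operated children is correct, as shown above. This stands, so there is no ground for barring the per-protocol repeat.
- **The denominators are not known.** A reader might infer that intra-operative percentages use every allocated child, including those never operated on. Table 10 does not say so. The remedy is to state the denominators.
- **Allocation is a legitimate basis for objective 5.** In a pragmatic treatment-policy trial, harm from later fixation in a child allocated to a cast is a consequence of the cast strategy, and Table 10 has a row for fixation or revision fixation. This stands, and the table by allocation should remain the main comparison.
- **Much can be recovered.** For cause-labelled rows, one can add the two columns and divide by the number operated on from Tables 8 and 9. This works in part. It fails for rows without a cause. Table 11 helps little, because it covers unexpected serious events potentially related to the intervention, while foreseeable complications go to Table 10.

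It might also be inferred that the SAP dropped a harms analysis promised in the protocol. The protocol's as-treated population was for the primary analysis only.

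**Conclusion.** The point holds as a cheap improvement. The comparison by allocation is sound and nothing is hidden. What is missing is a supplementary view of complications by treatment received. Without it, surgical harms in children who crossed from cast to surgery enter no rate among operated children, and the rows without a cause cannot be related to the treatment given.

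The size can only be illustrated. Over the assumed ranges it is about 0.4 to 6.7 surgical events in the cast column. It is small if few children switch, but for an uncommon harm one or two events in the other column can change how the table reads. The figures rest on assumed risks and switching rates, on no surgical complications in children not operated on and, except where stated, on equal risk in switchers.

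**What to change.** - Add a treatment-received safety population to SAP 4.2, with the grouping rule written down before unblinding. The rule should say where a child who starts in a cast and is operated on later belongs; grouping by first treatment alone would leave that child's surgical harms in the non-operative column.
- Present Table 10 for this population descriptively: counts, percentages and 95% confidence intervals, without p-values, labelled as a non-randomised comparison.
- For the intra-operative, wound and implant rows, use as denominator all children who had operative fixation up to 12 months, including later surgery in the cast arm.
- State the denominators in every version of Table 10.
- Keep the table by allocation as the main comparison. The per-protocol repeat may stay, but it should not be the only view of harms by treatment received.

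The cost is one definition and one extra table, from data already planned for Tables 8 to 10. The drawback is that the new table loses the protection of randomisation, hence the label.
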